9.1.2 Withdrawal of informed consent/ opposition to use data/biological samples

Patients may voluntarily withdraw consent to participate in the study for any reason at any time. Withdrawal of consent/ Opposition to use data/biological samples occurs only when a patient:

1. Explicitly requests to stop use of their biological samples and/or data (opposition to use patient's data and biological samples)

and

2. No longer wishes to receive study treatment

and

3. does not want to participate in the study any longer, and does not allow further collection of personal data.

This request should be in writing (depending on local regulations) and recorded in the source documentation.

Withdrawal of consent impacts ability to further contact the patient, collect follow up data (e.g. to respond to data queries) and potentially other country specific restrictions. It is therefore very important to ensure accurate recording of withdrawal vs. discontinuation based on the protocol definitions of these terms.

If a patient withdraws consent, the investigator should make a reasonable effort (e.g. telephone, e-mail, letter) to understand the primary reason for this decision to withdraw their consent/exercise data privacy rights and record this information. The investigator shall clearly document if the patient has withdrawn his/her consent for the use of data in addition to a study discontinuation.

Study treatment must be discontinued, and no further assessments conducted, and the data that would have been collected at subsequent visits will be considered missing.

Further attempts to contact the patient are not allowed unless safety findings require communication or follow up.

All efforts should be made to complete the assessments prior to study withdrawal. A final evaluation at the time of the patient's study withdrawal should be made as detailed in the assessment table.

For Japan: All biological samples not yet analyzed at the time of withdrawal may still be used for further testing/analysis in accordance with the terms of this protocol and of the informed consent form.

For EU and RoW: All biological samples not yet analyzed at the time of withdrawal will no longer be used, unless permitted by applicable law. They will be stored according to applicable legal requirements.

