12.1 Analysis sets

If the starting dose is different from the assigned dose level due to co-administration of ruxolitinib with strong CYP3A4 inhibitors or dual CYP3A4/CYP2C9 inhibitors, these patients will be included under the assigned dose level and considered that they have received the full assigned dose. This applies to Full Analysis Set, Safety Set and Efficacy Evaluable Set as described below.

The **Full Analysis Set (FAS)** comprises all patients to whom study treatment has been assigned and who received at least one dose of study treatment. Patients will be analyzed according to the treatment they have been assigned to.

The **Safety Set** includes all patients who received at least one dose of study treatment. Patients will be analyzed according to the study treatment received, where treatment received is defined as the assigned dose level of ruxolitinib if the patient took at least one dose of that treatment or the first dose level received if the assigned dose level was never received.

The **Pharmacokinetic Analysis Set (PAS)** includes all patients who provide at least one evaluable PK concentration. For a concentration to be evaluable, patients are required to:

1. Take the dose of ruxolitinib prior to PK sample.
2. For pre-dose samples, do not vomit within 2 hours after the dosing of ruxolitinib prior to sampling; for post-dose samples, do not vomit within 2 hours after the dosing of ruxolitinib.

The PAS will be used for Non-compartmental analysis (NCA) for patients where extensive PK sampling is obtained. This analysis set will also be used for any exposure-response analysis

The **Efficacy Evaluable Set** (EES) comprises all patients to whom study treatment has been assigned at the Recommended Phase 2 dose (RP2D) of ruxolitinib and who received at least one dose of study treatment at that dose level. If the starting dose is different from the RP2D due to co-administration of ruxolitinib with strong CYP3A4 inhibitors or dual CYP3A4/CYP2C9 inhibitors, these patients will be included in the EES.

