3.2 Analysis sets

If the starting dose is different from the assigned dose level due to co-administration of ruxolitinib with strong CYP3A4 or dual CYP3A4/CYP2C9 inhibitors, these patients will be included under the assigned dose level and considered that they have received the full assigned dose. This applies to all analysis sets described below.

The **Full Analysis Set** (FAS) comprises all patients to whom study treatment has been assigned and who received at least one dose of study treatment. Patients will be analyzed according to the treatment they have been assigned to.

The **Safety Set** includes all patients who received at least one dose of study treatment. Patients will be analyzed according to the study treatment received, where treatment received is defined as the assigned dose level of ruxolitinib if the patient took at least one dose of that treatment or the first dose level received if the assigned dose level was never received.

The **Pharmacokinetic Analysis Set** (PAS) includes all patients who provide at least one evaluable PK concentration. For a concentration to be evaluable, patients are required to:

- Take the dose of ruxolitinib prior to PK sample.
- For pre-dose samples, do not vomit within 2 hours after the previous dosing of ruxolitinib prior to sampling; for post-dose samples, do not vomit within 2 hours after the dosing of ruxolitinib.

The PAS will be used for Non-compartmental analysis (NCA) for patients where extensive PK sampling is obtained. This analysis set will also be used for any exposure-response analysis

The **Efficacy Eevaluable Set** (EES) comprises all patients to whom study treatment has been assigned at the Recommended Phase 2 dose (RP2D) of ruxolitinib and who received at least one dose of study treatment at that dose level. If the starting dose is different from the RP2D due to co-administration of ruxolitinib with strong CYP3A4 or dual CYP3A4/CYP2C9 inhibitors, these patients will be included in the EES.

All statistical analysis and data presentation for all analysis sets will exclude any data collected but not required as per study protocol. Data with a Protocol Deviation Code OTH11 (Other GCP deviation- Additional samples or Data collected not required as per protocol) will not be part of the analysis data or any output presentation.

Any patients who withdrew Informed Consent or from whom written Informed Consent was not obtained (Protocol Deviation INCL01) will be excluded from all analyses sets.

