Any data collected in the clinical database (other than acute GvHD biopsy, medical history, prior and concomitant medication, donor information, prior or concomitant non-drug therapies/procedures and viral load, serology from lab data, [REDACTED] and blood component transfusion) before signed of informed consent will not be included in the analysis. If a patient withdraws informed consent from all further participation in the trial no data will be included in the analysis after withdrawal of informed consent date. The informed consent date and the date on which a patient withdraws full consent are recorded in the eCRF.

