3.5.3 Handling of missing values/censoring/discontinuations

Patients with missing assessments that prevent the evaluation of the ORR will be considered non-responders. This includes aGvHD response assessments at baseline and Days 28, 56. Patients who discontinue the study treatment prior to the completion of the Day 28 visit will be considered non-responders.

The following analysis windows will be applied to the target day for assessments on overall response, where target day for Week X is X*7.

Baseline assessment is the last aGvHD assessment prior to or at the start of study treatment (Day 1).

Weeks 1, 2, 3, 4, 5, 6, 7, 8: -3 days/+3 days

Weeks 12 to 48: -13 days/+14 days

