3.6 Analysis of the key secondary objective

3.6.1 Key secondary endpoint

The key secondary objective of the study is durable ORR at Day 56.

Durable ORR at Day 56 is defined as the proportions of all patients who achieve a complete response (CR) or partial response (PR) at Day 28 and maintain a CR or PR at Day 56. If a patient is a CR at Day 28 and a PR at Day 56, he/she will be considered as a durable responder. A patient will not be considered a durable responder at Day 56 if any of the following events occurs:

- Not responder at Day 28
- Missing aGvHD assessment at Day 56
- No CR or PR at Day 56.
- additional systemic therapy for aGvHD prior to Day 56

Durable ORR will be calculated based on the FAS using local investigators review of aGvHD assessment data.

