Sample size	Minimum No. of responders	Response Rate	Probability to have a 90% CI with lower limit $\geq 60\%$	90% CI	
37	28	0.76	0.809	0.614	0.867
38	29	0.76	0.784	0.623	0.871
39	29	0.74	0.859	0.604	0.854
40	30	0.75	0.839	0.613	0.858
41	31	0.76	0.818	0.621	0.861
42	31	0.74	0.882	0.604	0.846
43	32	0.74	0.864	0.612	0.849
44	33	0.75	0.846	0.620	0.853
45	33	0.73	0.901	0.604	0.838
46	34	0.74	0.886	0.612	0.842
47	35	0.74	0.869	0.619	0.846
48	35	0.73	0.916	0.604	0.832
49	36	0.73	0.903	0.612	0.835
50	37	0.74	0.889	0.619	0.838

5 Change to protocol specified analyses

No change from protocol

6 Appendix

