6.1.2 AE, ConMeds and safety assessment date imputation

Table 5-1 Imputation of start dates (AE, CM) and assessments (LB, EG, VS)

Missing Element	Rule
day, month, and year	
 No imputation will be done for completely missing dates
day, month	
 If available year = year of study treatment start date then 
 If stop date contains a full date and stop date is earlier than study treatment start date then set start date = 01JanYYYY Else set start date = study treatment start date. If available year > year of study treatment start date then 01JanYYYY If available year < year of study treatment start date then 01JulYYYY
day	
 If available month and year = month and year of study treatment start date then 
 If stop date contains a full date and stop date is earlier than study treatment start date then set start date= 01MONYYYY. Else set start date = study treatment start date. If available month and year > month and year of study treatment start date then 01MONYYYY If available month and year < month year of study treatment start date then 15MONYYYY

Table 5-2 Imputation of end dates (AE, CM)

Missing Element	Rule (* if end date of the on-treatment period not > (death date, cut-off date, withdrawal of consent date))
day, month, and year	
 Completely missing end dates (incl. ongoing events) will be imputed by the end date of the on-treatment period*
day, month	
 If partial end date contains year only, set end date = earliest of 31DecYYYY or end date of the on-treatment period *
day	
 If partial end date contains month and year, set end date = earliest of last day of the month or end date of the on-treatment period*

Any AEs and ConMeds with partial/missing dates will be displayed as such in the data listings.

Any AEs and ConMeds which are continuing as per data cut-off will be shown as 'ongoing' rather than the end date provided.

The above imputations are only used for analyses of time to and duration of AEs and concomitant medications.

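### SAP 3.2 gives two incompatible rules for patients who withdraw consent: one removes the patient from every analysis set, the other removes only the data after withdrawal

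*SAP*

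**What the plan says.** SAP 3.2 (Analysis sets) handles consent in two adjacent paragraphs.

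- The first removes the patient: "Any patients who withdrew Informed Consent or from whom written Informed Consent was not obtained (Protocol Deviation INCL01) will be excluded from all analyses sets".
- The second concerns a patient who withdraws consent from all further participation. It removes only later data: "no data will be included in the analysis after withdrawal of informed consent date". It adds that the withdrawal date is recorded in the eCRF.

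Other text bears on the same patients:

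- SAP 6.1.2, Table 5-2 uses the withdrawal date to limit imputed end dates of adverse events and medications: "if end date of the on-treatment period not > (death date, cut-off date, withdrawal of consent date".
- SAP 3.5.3: "Patients with missing assessments that prevent the evaluation of the ORR will be considered non-responders". Stopping treatment before the Day 28 visit is completed also counts as non-response there.
- SAP 3.6.1 lists "Missing aGvHD assessment at Day 56" among the reasons a patient is not a durable responder.
- Protocol 9.1.2, on visits after withdrawal: "the data that would have been collected at subsequent visits will be considered missing".
- Protocol 12.1 defines the EES by dose assigned and received; it "comprises all patients to whom study treatment has been assigned at the Recommended Phase 2 dose (RP2D) of ruxolitinib" and who took at least one dose at that level. The FAS and Safety Set are likewise defined by treatment, and none of the three excludes patients for withdrawing consent.
- SAP Section 5, on departures from the protocol: "No change from protocol".

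**The concern.** Read literally, the first rule takes a treated child who withdraws consent at any time out of the FAS, Safety Set, PAS and EES. The second leaves that child in and cuts the record at the withdrawal date. Two programmers working from SAP 3.2 could therefore build different denominators for the primary ORR.

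The distortion has no fixed direction:

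- A child who withdraws before Day 28 should count as a non-responder. Under the first rule that child leaves the denominator and the ORR is too high.
- A Day 28 responder who withdraws later has a valid primary outcome. Under the first rule it is discarded and the ORR is too low.
- In either case, adverse events recorded before withdrawal leave the Safety Set, although Protocol 12.1 puts every treated patient in it.

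There is no slack to absorb this. The rationale for protocol amendment 3 reports enrollment closed at 45 patients, exactly the target, and Protocol 9.1.1.1 does not replace patients who discontinue.

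Only formal withdrawal of consent is affected. Patients who stop treatment, are lost to follow-up or die before Day 28 stay in the EES as non-responders under either reading.

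**Working it through.** **1. Can the two paragraphs be reconciled?**

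- *By the code INCL01.* If it governed the whole sentence, only patients without consent at entry would be excluded. But the sentence joins withdrawal and absence of written consent with an *or*, so withdrawal is a separate ground.
- *By scope.* The first paragraph might mean opposition to data use, and the second withdrawal from further participation only. The SAP draws no such line, and Protocol 9.1.2 puts both into one definition of withdrawal.

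Neither reading works without words the SAP does not contain.

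**2. Which rule does the rest of the plan assume?** Table 5-2 needs a withdrawal date only if withdrawn patients are analyzed. Protocol 9.1.2 makes later visits missing, and SAP 3.5.3 and 3.6.1 turn a missing Day 28 or Day 56 assessment into non-response. Protocol 11.4 says information collected before a revocation of authorization may still be used. All of this fits the second rule.

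**3. The plan's own figure.** Inputs from SAP Section 4 and Protocol 12.8.1: n = 45, true ORR 80%, two-sided 90% Clopper-Pearson interval, target lower limit 60%. For x responders out of n:

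- lower limit = 5th percentile of Beta(x, n − x + 1)
- upper limit = 95th percentile of Beta(x + 1, n − x)

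At n = 45 the smallest x with a lower limit of at least 60% is 33 (interval 0.604 to 0.838). P(X ≥ 33 | 45, 0.80) = 0.9005, which reproduces the 0.901 in SAP Table 4-1 and Protocol Table 12-2.

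**4. The two rules compared.** The withdrawal counts are assumed, because the documents give none.

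| Assumed case | Patient kept | Patient removed |
|---|---|---|
| 32 responders, 2 withdraw before Day 28 | 32/45 = 71.1% (58.0 to 82.0) | 32/43 = 74.4% (61.2 to 84.9) |
| 36 responders, 2 withdraw before Day 28 | 36/45 = 80.0% (67.7 to 89.2) | 36/43 = 83.7% (71.6 to 92.1) |
| 33 responders, 1 of them withdraws after Day 28 | 33/45 = 73.3% (60.4 to 83.8) | 32/44 = 72.7% (59.6 to 83.5) |

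**5. When does the lower limit change sides of 60%?** The minimum responder counts are 33 of 45, 33 of 44, 32 of 43 and 31 of 42.

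- Removing early withdrawals moves the limit above 60% when the count is below 33 but reaches the minimum for the smaller n. That happens at no count with one withdrawal, only at 32 with two, and only at 31 or 32 with three.
- Removing one responder moves it below 60% only when 33/45 becomes 32/44.

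**6. Effect on the design probability.** Suppose k patients withdraw before Day 28 and the other 45 − k respond at 80%. If the k are kept as non-responders, 33 responders are still needed. If they are removed, the minimum is that for n = 45 − k.

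| k | Kept | Removed |
|---|---|---|
| 1 | 0.846 | 0.846 |
| 2 | 0.771 | 0.864 |
| 3 | 0.676 | 0.882 |
| 5 | 0.437 | 0.839 |

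**The case against.** The best argument for the exclusion is the protocol's own definition. Under Protocol 9.1.2 and the glossary, withdrawal of consent includes a request to stop use of data or samples. A patient who merely stops treatment falls in a separate category. Removing such patients entirely could therefore be a deliberate choice by the sponsor. It is not the choice the rest of the plan makes, however. Protocol 9.1.2 treats only later visits as missing, Protocol 11.4 allows use of earlier information, and SAP 3.2 itself goes on to cut the data at the withdrawal date. What stands is that local law may bar use of earlier data for some patients, and the fix has to allow for that.

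A second argument is that the intent can be recovered. INCL01 is a missing-consent code, and the SAP's amendment history says all patients who signed consent were included. This makes the second rule the likelier intention, but the sentence as written can still be programmed literally.

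A third is that the effect is hypothetical and small: a few percentage points inside an interval about 24 points wide, with the 60% limit crossed only at particular counts. That is correct. The trial also tests no hypothesis, and 60% is the sizing target, not a success criterion. These points limit the size of the problem; they do not settle which rule applies.

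**Conclusion.** The contradiction is real and should be fixed. Followed literally, the exclusion sentence gives EES and Safety Set denominators that conflict with Protocol 12.1, and Section 5 does not declare the departure.

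In the assumed cases the ORR rises by 3.3 to 3.7 points with two early withdrawals and falls by 0.6 points when one responder withdraws later. All these cases take n = 45, withdrawals before Day 28 counted as non-response when kept, and withdrawal counts chosen for illustration. If nobody withdrew, no result changes. What is affected is the estimate, its interval and the safety denominators; no type I error is involved. Confidence is high that the wording conflicts. The effect on the actual results cannot be known from the documents.

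**What to change.** 1. In the SAP 3.2 exclusion sentence, strike the reference to patients who withdrew consent. The all-sets exclusion then covers only patients without valid written consent (INCL01).
2. List that remaining exclusion in SAP Section 5, since Protocol 12.1 does not contain it.
3. State that treated patients who later withdraw stay in every set for which they qualify, with data up to the withdrawal date. Withdrawal before the Day 28 or Day 56 assessment then counts as non-response under SAP 3.5.3 and 3.6.1, and no new endpoint rule is needed.
4. Where opposition to data use legally bars use of earlier data, report how many patients were removed. Where the law allows them to be counted, add a sensitivity analysis that scores them as non-responders. Describe it as a conservative bound, because it also scores as a failure any patient who had responded at Day 28.

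The cost is a short SAP edit and possibly one extra table, with no new data. Compared with the literal rule, the reported ORR would be lower if withdrawals came before Day 28 and higher if responders withdrew later.

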3.2.1 Subgroup of interest

Efficacy

The primary efficacy endpoint will be summarized by the following subgroups to examine the homogeneity of treatment effect using EES:

- Age group (range defined in [Table 1-1](#))
- Age group and formulation (tablet, capsule, liquid)
- Diagnosis (treatment naïve aGvHD and SR-aGvHD)
- [REDACTED] No formal statistical test of hypotheses will be performed for the subgroups, only point estimate of the treatment effect and 90% confidence intervals will be provided.

Safety

Key safety analyses will be repeated on the Safety Set in the following subgroups:

- Age group (range defined in [Table 1-1](#))
- Age group and formulation (Tablet, capsule, liquid)
- Diagnosis (treatment naïve aGvHD and SR-aGvHD)
- [REDACTED]

The objective for carrying out these subgroup analyses is to identify potential safety issues that may be limited to or more commonly observed in a subgroup of patients.

The following summaries will be presented by age group, formulation and [REDACTED] only subgroup:

- Overview of adverse events
- Adverse events by preferred term
- Adverse events with suspected relationship to study treatment by preferred term
- Serious AEs, irrespective of causality, by preferred term
- Adverse events leading to study treatment discontinuation by preferred term
- Overview of adverse events of special interest
- On-treatment deaths
- All study deaths

The following summaries will be provided by age group and and by treatment-naive vs SR aGvHD:

- Overview of adverse events
- AEs, irrespective of causality, by primary system organ class and preferred term
- AEs with suspected relationship to study treatment, by primary system organ class and preferred term
- Serious AEs, irrespective of causality, by primary system organ class and preferred term
- Serious AEs with suspected relationship to study treatment, by primary system organ class and preferred term
- On-treatment deaths, by primary system organ class and preferred term
- Overview of adverse events of special interest

